## 11.4. MISSING DATA/SAP DEVIATIONS

The intent is to collect as complete a dataset as possible. Nevertheless, in some situations missing data cannot be avoided. The reports and tables therefore will show the number and percentage of missing cases for each analyzed variable in relation to the enrolled cases for each postoperative assessment.

Any deviations from the SAP will be listed in the annual or final reports.

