## 9.3. WITHDRAWAL CRITERIA

If during the clinical investigation a subject must be prematurely withdrawn, then the procedures outlined in this section must be followed. These procedures should not interfere with the initiation of any new treatments that are necessary to treat a subject's condition. Information on all withdrawn subjects will be documented.

Subjects may be withdrawn from the clinical investigation for any of the following reasons:

- Subject Withdrawal: A subject may voluntarily withdraw from the clinical investigation at any time and for any reason. The subject should be asked when possible, and without any form of coercion, the reason for his/her decision. If the participant withdraws from the clinical investigation completely, then data collected up until the point of withdrawal will be included in the final analysis.

- ii. Lost to Follow-Up (LTFU): A subject will be considered LTFU after all reasonable efforts have been made to contact the subject and request his/her continued participation in the clinical investigation. All attempts to contact the subject must be documented and should include at least two attempts to contact the subject by phone and one attempt via a certified letter. Data collected up until the point where the subject is LTFU will be included in the final analysis.
- iii. Removal of Device or AE/Incident: The discontinuation of a subject's participation in the clinical investigation due to the removal of the ReUnion RFX System or AE/incident that prohibits his/her continued participation must be fully explained. All available information concerning the removal of the device or AE/incident should be provided. Data collected up until the point of removal or AE/incident will be included in the final analysis.
- iv. Death: The discontinuation of a subject's participation in the clinical investigation due to death must be fully explained. All available information concerning the death or AE should be provided. Removal of a subject from continued follow-up in the clinical investigation due to death will not be considered a device failure unless the death is directly caused by, or attributable to, the ReUnion RFX System. Data collected up until the point of death will be included in the final analysis.

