### **10.3. FOLLOW-UP EVALUATIONS**

Subjects in this clinical investigation will be evaluated at Preoperative, Operative/Discharge, and at 6 Weeks (4 weeks – 8 weeks), 6 Months (24 weeks – 28 weeks), 12 Months (48 weeks- 56 weeks), 24 Months (100 – 108 weeks) and annually thereafter. The follow-up evaluations will include assessment of device-related AEs/incidents, radiographs and ASES Shoulder Score.

Investigative site personnel will contact subjects prior to their scheduled follow-up evaluations to encourage compliance with clinical investigation visits and participation.

If a subject misses a visit and is outside of the visit window, every effort should be made to collect data instead of noting the visit as missed.

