#### 10.4. SCHEDULE OF EVENTS

Assessment	Pre-Operative	Operative/ Discharge	6 Weeks a, b (+/- 2 weeks)	6 Months a, b (+/- 3 weeks)	12 Months a, b (+/- 4 weeks)	24 Months a, b (+/- 4 weeks)	Annually b (+/- 4 weeks)
Informed Consent	X						
Demographics & Medical History	X						
Inclusion/Exclusion	X						
Physical Exam	X		X c	X c	X c	X c	X c
Surgical Procedure		X					
ASES Shoulder Score	X		X d	X d	X d	X d	X d
Image Evaluation e, f	X	X	X	X	X	X	X
Subject Disposition g			X	X	X	X	X
	Device-Related AEs/Incidents & Reoperations will be collected throughout the course of the clinical investigation.						
	
 
a. Follow-up visit schedule to reflect Institution's Standard of Care practices
 
b. If the subject misses a visit and is outside of the visit window, then every effort should be made to collect data instead of noting visit as missed. Visit windows are calculated from index event, and not from previous visit.
 
c. Evaluation may be collected when subject presents in-clinic for study visit.
 
d. Evaluation can be collected via phone.
 
e. Radiograph collection should follow Institution's Standard of Care practices and no additional x-rays should be made for study purposes.
 
f. CT scans may be collected if part of Institution's Standard of Care practices.
 
g. Subject Disposition assessment will occur at any time point for subject withdrawal prior to the completion of the clinical investigation.
 
						

Table 1: Schedule of Events

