#### IBM SPSS Sample Power Output – Screenshot

Estimated overall drop-out rate is 56% which leads to the requirement of enrolling an additional 6 subjects into the clinical investigation.

Sample Size	Overall number of subjects to be enrolled: 16 subjects (rounded up to 20 subjects)
Overall Sample Size (multiplied by number of indications = 5)	100 subjects

Table 2b: Sample Size Justification (RSA)

In conclusion, the calculated number of subjects to be enrolled (10) plus the estimated overall drop-out rate of 56% predicts enrollment of 16 subjects (rounded up to 20) per indication. Since the five cleared indications and the proposed sample sizes are identical for the two clinical investigation arms, the sample size of one indication ( $n=20$ ) will be multiplied by five to reflect the total underlying subject population adequately. As a result, an enrollment target of 100 subjects in total will be aspired (ideally, but not necessarily, composed with 20 subjects per indication).

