### 11.3.2. Primary Analysis / Endpoint

The objective of the clinical investigation is to demonstrate the non-inferiority (equal or better) of the ASES Shoulder Score in relationship to the officially cleared indications in comparison to respective clinical outcome data in the scientific literature.

Data collection of ASES Shoulder Score will be collected according to the schedule in Table 1, Schedule of Events. This will be repeated annually in all subjects who have the prosthesis with full or partial implant survival (including all subjects without removal of all endo-prosthesis components).

The 24 months postoperative results for subjects implanted with ReUnion RFX System will be compared to a historical group and results reported by respective clinical outcome data in the scientific literature.

[figure not shown]
Higher ASES Shoulder Score results are linked to better subject results and vice versa.

The clinical investigation endpoint is non-inferiority to the control, meaning the clinical investigation result should be equal or better than the control. In this clinical investigation, an equal or better ASES Shoulder Score result means equal or more ( $\geq$ ). As only results from samples will be captured, results are mostly estimates of the true population parameter. These

estimates vary by a certain area, where it is expected that the true population parameter falls within. Based on this, it is required to specify a lower limit for the acceptable difference or zone of indifference, denoted as  $-\theta$ .

Hypotheses are developed to allow for a comparison of the 24 months postoperative ASES Shoulder Score effectiveness/performance between the two underlying populations. The 24 months post-operative ASES Shoulder Score is the primary endpoint of this clinical investigation. Hypothesis tests will be one-sided with a significance level  $\alpha$  of 5%.

[figure not shown]
Table 3a: Arm A (TSA/HA)

Hypothesis	Equations	Interpretation
Null ( $H_0$ )	$A - B < -\theta$	Central tendency of A is inferior to the central tendency of B.
	ReUnion RFX System (TSA/HA) – Control (Benchmark) $< -\theta$	
Alternative ( $H_1$ )	$A - B \geq -\theta$	Central tendency of A is non-inferior to the central tendency of B.
	ReUnion RFX System (TSA/HA) – Control (Benchmark) $\geq -\theta$	
		
Possible Evidence (p)	Possible Decisions	Possible Conclusions – ASES score

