4.4. TIMING OF OUTCOME ASSESSMENT

Subjects in this clinical investigation will be evaluated at Pre-Operative, Operative/Discharge, and at 6 Weeks (4 weeks – 8 weeks), 6 Months (24 weeks – 28 weeks), 12 Months (48 weeks- 56 weeks), 24 Months (100 weeks – 108 weeks) and annually (up to ten years) after the index procedure. The follow up evaluations will include assessment of complications and adverse events and ASES Shoulder Score.

Assessment	Pre-Operative	Operative/ Discharge	6 Weeks ^{a, b} (+/- 2 weeks)	6 Months ^{a, b} (+/- 3 weeks)	12 Months ^{a, b} (+/- 4 weeks)	24 Months ^{a, b} (+/- 4 weeks)	Annually ^b (+/- 4 weeks)
Informed Consent	X						
Demographics & Medical History	X						
Inclusion/Exclusion	X						
Primary Diagnosis	X						
Surgical Procedure		X					
ASES Shoulder Score	X		X	X	X ^c	X ^c	X ^c
Subject Disposition ^d			X	X	X	X	X
	Device-Related AEs/Incidents & Reoperations will be collected throughout the course of the clinical investigation.						
	a. Follow-up visit schedule to reflect Institutions’ Standard of Care practices b. If the subject missed a visit and outside of visit window, every effort should be made to collect data instead of noting visit as missed. Visit windows are calculated from index event, and not from previous visit. c. Evaluation can be collected via phone. d. Subject Disposition assessment would occur at any time point for subject withdrawal prior to the completion of the clinical investigation.						

Table 4.4: Schedule of Events

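### The primary 24-month ASES test in effect uses observed scores only: missing scores are counted but not handled, no rule says how full explants count, and the documents disagree on which report carries the test

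*Protocol*

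**What the plan says.** **Missing scores.** Protocol 11.4 commits to reporting, not handling: "The reports and tables therefore will show the number and percentage of missing cases for each analyzed variable". SAP 4.6 repeats this. SAP 6.6 applies a one-sample t-test or sign test to the 24-month total ASES, with no imputation, model or failure value.

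**Explants.** Protocol 11.3.2 and SAP 3.1.1 say that ASES collection is repeated annually "in all subjects who have the prosthesis with full or partial implant survival (including all subjects without removal of all endo-prosthesis components". Protocol 9.3 iii, on discontinuation because of device removal or an adverse event, says: "Data collected up until the point of removal or AE/incident will be included in the final analysis".

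**Safeguards.** For a missed visit, Protocol 10.3 says "every effort should be made to collect data instead of noting the visit as missed", and SAP 4.4 says "every effort should be made to collect data instead of noting visit as missed". The Protocol 10.4 footnote on ASES reads "Evaluation can be collected via phone"; SAP 4.4 also allows the phone at month 24. Contact attempts before a subject is declared lost "should include at least two attempts to contact the subject by phone and one attempt via a certified letter" (Protocol 9.3 ii). If anyone is excluded from the per-protocol (PP) set, ITT and PP are both analysed (Protocol 11.2, SAP 5.1).

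**Attrition.** The sample-size tables state: "Estimated overall drop-out rate is 56" per cent. The source cited is a follow-up at a minimum of 10 years.

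**Reporting.** Protocol 11.5.1 and SAP 4.2 place the primary analysis in the annual report issued once all subjects have completed 24 months. SAP 6.6 places it in the final report. ITT is analysed in the final report only, and PP exclusions are settled after the investigation is completed.

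**The concern.** A one-sample comparison with a fixed limit has no second arm in which losses could offset. If subjects whose shoulders did badly are less likely to have a 24-month score, the observed mean rises and the limit does not move. Losing low scorers can therefore push the result only towards non-inferiority. Counting missing cases shows the size of the gap but not whether the conclusion survives it.

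The explant wording adds to this. It implies that a subject with all components removed is not scored, and nothing says whether that subject then counts as a failure, at the last value, or not at all. Such failures would still appear under adverse events, reoperations and the Kaplan-Meier analyses, but not in the primary test.

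The reporting conflict is a separate problem. If the test sits in an annual report, it appears without ITT and before the PP review. PP exclusions, one ground for which is a judgement that a deviation probably influenced outcome, would then be decided with the 24-month scores already known.

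**Working it through.** **Inputs from the documents** (Protocol 11.1 and 11.3.2). Arm A: benchmark mean 58.74, SD 20.33, limit 58.74 − 20.33 = 38.41. Arm B: 74.48, 11.08, limit 74.48 − 11.08 = 63.40. One-sided 5% test. As a check on these inputs, the stated 80.3% power at n = 10 reproduces (noncentral t, effect size 1.0, two-sided 5%: 0.8031).

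**Assumptions, not in the documents.** 50 subjects per arm; the plan's SD among completers; the t-test; and the missingness and score deficits shown below.

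**1. True mean at the limit.** If a fraction f is unscored and averages D points below completers, the completers' mean exceeds the full-cohort mean by f × D.
- Low case: 0.05 × 20 = 1.0 point. High case: 0.10 × 30 = 3.0 points.
- With the full-cohort mean exactly at the limit, P(pass) = P(noncentral t, df 44, ncp = bias × √45 / SD, exceeds 1.680). The number of completers is held at 45 in both cases.
- Arm B: ncp 0.605 gives 14.7%; ncp 1.816 gives 55.7%.
- Arm A: ncp 0.330 gives 9.3%; ncp 0.990 gives 25.1%.
- The nominal rate is 5%.

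**2. Completers at the benchmark.** With N subjects, m missing, completers' mean μ and SD s, and each missing score set to μ − D:
- Mean = μ − D·m/N
- SD² = [(N−m−1)s² + (N−m)(μ−Mean)² + m(μ−D−Mean)²]/(N−1)
- t = (Mean − limit)·√N / SD

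Worked case, Arm B, 13 of 50 missing, D = 30:
- Mean = 74.48 − 7.80 = 66.68
- SD² = [36 × 11.08² + 37 × 7.80² + 13 × 22.20²]/49 = 266.9, so SD = 16.34
- t = 3.28 × 7.071/16.34 = 1.42, p = 0.081

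Other cases:

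| Arm | Missing | Missing scores set to | Result |
|---|---|---|---|
| B | 5 of 50 | 30 below completers | p = 0.00007 |
| B | 5 of 50 | 60.6 below (score 13.9) | tips |
| A | 5 of 50 | 0 | p = 0.00015 |
| A | 11 of 50 | 0 | p = 0.046 |
| A | 12 of 50 | 0 | p = 0.080 |
| B | 8 of 50 | 41.8 below (score 32.7) | tips |
| B | 12 of 50 | 30 below | p = 0.048 |
| B | 19 of 50 | 20 below | p = 0.033 |
| B | 20 of 50 | 20 below | p = 0.051 |
| A | 15 of 50 | 46.2 below (score 12.5) | tips |

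In a smaller arm, 3 of 20 missing tips Arm B at 33.1 below (score 41.4). At 28 of 50 missing (56%), Arm B tips at 15.3 below and Arm A at 28.1. Filling one value ignores spread among the missing, so true tipping comes slightly earlier.

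**3. The sign-test branch.** The plan switches to the sign test when normality fails, and a block of identical filled values will usually make it fail. With normal completers at the benchmark, Φ(1) = 0.841 of them exceed the limit.
- Arm B, 8 missing: 42 × 0.841 ≈ 35 of 50 above 63.40, p ≈ 0.003 for any filled score below the limit.
- 12 missing: about 32 of 50, p = 0.032. 13 missing: about 31 of 50, p = 0.059.

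On this branch, once the shift exceeds 11.08 points, the result depends on how many scores are missing and not on how low they are.

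**The case against.** The strongest reply is that few low scores are lost by design. Subjects with partial implant survival stay in ASES collection, and the system is meant to allow later conversion on a well-fixed stem (Protocol 6). The out-of-window and phone provisions carry no exception for revised subjects. Missingness is shown against enrolled cases. On the plan's own means, 5 missing of 50 does not threaten either arm at plausible deficits, and Arm A passes even with 11 of 50 scored zero. All of this stands, and it limits the size of the concern. It does not supply a rule for full explants, or any test of the conclusion if missingness turns out higher.

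Two further objections stand and shape the fix. The tipping figures depend on the t-test: the Arm B case with 8 of 50 missing disappears under the sign test. And filling scores for everyone implanted would give deceased subjects a poor ASES, although Protocol 9.3 iv does not treat death as a device failure unless it is attributable to the device.

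A reader might infer more than the documents support:
- **That they are silent on whether explants are scored.** Protocol 11.3.2 and SAP 3.1.1 imply that full explants are not, although the wording is attached to the annual repeats. The gap is how they count in the primary test.
- **That removal ends data collection.** Protocol 9.3 says subjects may be withdrawn, and item iii keeps data up to that point; it does not say that removal stops follow-up automatically.
- **That no second analysis exists.** ITT beside PP is planned if there are exclusions. It has no missing-data rule, so a missing score is missing in both sets.
- **That 56% will be missing at month 24.** That figure rests on a source with at least 10 years of follow-up.

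**Conclusion.** The concern holds in limited form. The primary test in effect uses observed scores only (the documents do not use the term complete-case), no sensitivity analysis for missing scores is planned, and no rule says how full explants count. The direction of any bias from lost low scorers is known; its size is not.

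On the plan's means and SDs the result is robust at about 10% missing (5 of 50). It could change in Arm B at higher missingness: under the t-test, from 13 of 50 (26%) at 30 points below completers, or 20 of 50 (40%) at 20 below. It could also change if the Arm B mean is near 63.40. The false-pass rates of 15–56% (Arm B) and 9–25% (Arm A) apply only with a true mean exactly at the limit and are not forecasts. Missingness, failure scores and the arm split are all assumed.

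The conflict between Protocol 11.5.1 with SAP 4.2 and SAP 6.6, and the late PP review, need no such assumptions. The plan should be amended on both matters; the primary test, limits and sample size need not change for this.

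**What to change.** 1. State that the 24-month ASES is sought, by phone if needed, from every implanted subject who is alive and has not withdrawn consent, including after removal or revision. State how explanted subjects count in the primary test.
2. Beside the primary test, pre-specify a shift (tipping-point) analysis by arm over implanted subjects alive at 24 months. This set differs from the documents' ITT population. Use the one-sample t-test whatever the normality result. Multiply impute missing scores around the completers' mean minus 0, 10, 20, 30 and 40 points, and onward until the result tips or the score reaches 0. Report deaths separately, with device-attributable deaths handled consistently with Protocol 9.3 iv.
3. Reconcile Protocol 11.5.1 and SAP 4.2 with SAP 6.6, and report ITT in whichever report carries the primary test.
4. Fix the PP exclusion list for the primary analysis before 24-month ASES results are tabulated.

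The cost is wording in both documents, a few extra phone questionnaires and one added analysis. The mean may come out less favourable, and may be less comparable with the benchmark if those studies left out failures, which the documents do not show.

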## 11.5. REPORTS

### 11.5.1. Interim Analysis and Reports

Interim analyses will be performed on a yearly basis. The progress of the clinical investigation will be reported together with the interim results on the variable level according to the analysis plan.

The analysis of the primary endpoint will be part of the related interim/annual report when all subjects have completed the 24 months postoperative including the ASES Shoulder Score.

### 11.5.2. Final Analysis and Reports

The full final report with complete analysis including progress and conduct reporting will be created at the end of this clinical investigation.

## 12. Clinical Investigation Plan Deviations

A CIP deviation is a departure from the approved CIP that is not implemented or intended as a systemic change. All CIP deviations are recorded and reported to each site's IRB in accordance with the respective site's IRB policies.

## 13. Adverse Events

As this CIP is being carried out to satisfy the post-market requirements to support safety and efficacy/performance according to the European Medical Device Regulation (EU MDR), categorization and definition of device-related AEs will follow the guidelines outlined in the EU MDR as "incident" reporting.

### 13.1. DEFINITIONS

- **An Adverse Device Effect (ADE)** is defined as any untoward or unintended response to the clinical investigation treatment; and/or a medical response which may have a causal relationship to the treatment.
- **An Incident** is defined as any malfunction or deterioration in the characteristics or performance of a device made available on the market, including use-error due to ergonomic features, as well as any inadequacy in the information supplied by the manufacturer and any undesirable side-effect.
- **A Serious Adverse Device Effect (SADE)** is defined as any ADE that results in consequences characteristic of a SAE or might lead to the consequences if suitable action or intervention is not taken; causes considerable interference with the subject's usual activities and may be incapacitating or life-threatening, including those events resulting in a subject's disability or permanent damage, or required intervention to prevent disability or permanent damage; results in a life-threatening illness or injury; and/or results in death (fatal).
- **A Serious Incident** is defined as any incident that directly or indirectly led, might have led or might lead to any of the following:
  - the death of a patient, user or other person;
  - the temporary or permanent serious deterioration of a patient's, user's or other person's state of health;
  - a serious public health threat
- **An Unanticipated Adverse Device Effect (UADE)** is defined as an AE not described in the informed consent, CIP or device labeling which has resulted in any of the consequences of a SAE or which might have led to any of the consequences of a SAE if suitable action had not been taken, intervention had not occurred, or if circumstances had been less opportune.

### 13.2. ADVERSE EVENT SEVERITY

The severity of all AEs is assessed by the Investigator utilizing the following categories:

- **Mild:** The AE is transient and easily tolerated by the subject.
- **Moderate:** The AE causes the subject discomfort and interrupts the subject's usual activities.
- **Severe:** The AE causes considerable interference with the subject's usual activities and may be incapacitating or life-threatening, including those events resulting in a subject's disability or permanent damage, and/or required intervention to prevent permanent disability or damage.
- **Life-Threatening:** The AE results in a life-threatening illness or injury.
- **Fatal:** The AE results in death.

### 13.3. RELATIONSHIP TO THE DEVICE

Only events considered possibly, probably or definitely related to the device will be captured for this clinical investigation.

### 13.4. ADVERSE EVENT/INCIDENT REPORTING

In the event a SADE, UADE or serious incident occurs, the Investigator is required to notify the Sponsor within 48 hours of being made aware of the event. The Investigator also is required to notify their IRB in accordance with the policies of their local laws and regulations.

